Our group has shown that central circadian rhythm disruption (of light:dark cycles) enhances mucosal inflammation in animal model of chemically induced-colitis. Also, disruption of central circadian rhythmicity induced by changing light:dark cycles combined with alcohol disrupted intestinal barrier integrity and promoted gut leakiness to endotoxins, a situation that promotes mucosal and systemic inflammation. My novel and exciting preliminary data in mice show that disruption of intestinal circadian homeostasis by an abnormal eating pattern [“wrong time eating”] accelerates the development of alcohol-induced colon cancer [Fig 1]. Further, the abnormal eating pattern shifted the colonic circadian rhythm [Fig 2]. Accordingly, the objectives of my K23 application are (i) to test the hypothesis that *a delayed eating pattern is a key cofactor that increases susceptibility to alcohol-induced colon carcinogenesis* and (ii) to elucidate the mechanism. This is significant as the first step to better understand how disruption of intestinal circadian rhythms by delayed eating patterns promote alcohol-associated colonic neoplasia. This will have immediate impact in risk

stratification of alcohol consumers for CRC screening, and can be readily extended to the general population in tailoring primary and secondary prevention strategies. Outcomes from these studies will lead to in-depth mechanistic studies and ultimately the discovery of novel targets to prevent CRC. Also, this study will have implications in a broader range of alcohol-related pathologies that are the consequence of gut inflammation.

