## B. INNOVATION

In this era of personalized/precision medicine, it is prudent to identify host factors that promote alcohol-induced colon carcinogenesis. This project will establish an **innovative discovery**: that delayed eating patterns ("wrong time eating") is a risk factor for alcohol-induced colon carcinogenesis pathways in human. Our prelim data support the promoting role of wrong time eating in alcohol-induced polyposis [Fig 1]. Our **hypothesis** –intestinal circadian dyssynchrony due to delayed eating results in pro-tumorigenic inflammatory profile, associated with enhanced carcinogenesis in susceptible host – is novel. Our translational **experimental approach is innovative**. We will use a combination of animal and human studies – In subjects with history of advanced sigmoid/descending colon polyps, we will assess : (i) Central circadian rhythms by hourly salivary melatonin; (ii) and "Digestive tract" circadian rhythm by 2 hourly buccal and 12 hourly rectal expression of clock genes. This will provide valuable information regarding the impact of eating patterns and alcohol consumption on central and peripheral circadian rhythms and the relationship of these inter-related, yet independent circadian biosystems. Our human study will use a crossover, 2 by 2, design to examine the same individual under 4 conditions ( $\pm$  delayed eating pattern &  $\pm$  alcohol). Using a crossover design will eliminate inherent inter-individual variations in alcohol metabolism, circadian rhythm, immune system, and microbiota composition. This design will allow for use of smaller sample size and for a more accurate examination of the impact of alcohol and eating conditions on the circadian system and its interaction with mucosal immune profiles, microbiota and carcinogenesis markers. Our **data analysis approach is state of the art and innovative** as we will use systems biology and network analysis specifically transcriptional profiling to assess the effects of alcohol and eating patterns on our outcomes (immune profiles, circadian synchrony, microbiota data, and carcinogenesis markers), and to characterize profiles associated with each experimental condition. We will first establish an **innovative pro-tumorigenic immune mucosal profile** based on RNA-based signatures of our established animal model. We will identify transcriptional profiles in the colonic mucosa that include immune response genes and which are specifically expressed upon occurrence of polyp/cancers. We will use this RNA seq profile and integrate these signatures with other measures collected in this project to assess the impact of food intake patterns on alcohol-associated changes in endoscopic colon mucosal samples in patients, particularly in immune response genes [Aim 3] [Fig. 3]. This **innovative multidisciplinary approach** is possible due to the combined efforts of the five mentors who are well-established investigators in complementary areas of research with previously established collaborative research efforts among them. The mentors were chosen based on their areas of expertise: [name] lab [my primary mentor and chair of my mentorship committee], direct molecular and cellular mechanisms that underlie alcohol-induced and circadian rhythm disruption effects on the intestine; [name] lab, measurements of circadian rhythms in humans; [name] lab, mucosal inflammation in polyposis and cancer; [name] lab, RNA-sequencing; [name] lab, systems biology. The goal of this K23 application is to take an integrated approach with mentors from different fields. Their combined expertise will guarantee a successful completion of the proposed studies, and, will provide a unique environment for training the applicant as an independent translational physician-scientist in the field of chrono-oncology and alcohol.

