Fig 3: The RNA seq data from colon mucosa of B6 animals will be used to identify the immune Th17/Treg/Neutrophil profile associated with alcohol, wrong time eating or both. This profile will be refined by looking at polyp-based RNA-seq data in APC mice, to subside the immune signature to pathways predictive of colon carcinogenesis. In the next step, cancer predictive profile in the adjacent mucosa predictive of polyp profile will be determined. This profile will be used for Aim3.

different sleep/wake cycles on the weekend vs. weekdays, present in at least 30% of western populations). Delayed eating is an understudied life-style factor and yet the main energy contributor in industrialized countries is dinner, that is close to the rest time. Food timing is the main regulator of the circadian of the digestive tract. Our data from a mouse model of polyposis (Fig 1) indicate that wrong time (rest time) eating promotes alcohol-induced colon carcinogenesis. In this proposal, we will determine the effect of the combination (as well as each separately) of alcohol consumption and delayed eating on colonic mucosal inflammation, microbiota and markers of carcinogenesis in susceptible subjects for CRC. My Project will determine role of delayed eating in (1) exacerbation of alcohol-induced mucosal inflammation; (2) promotion of colon carcinogenesis after modest alcohol intake and elucidate the mechanism involved. My proposed studies will lead to identification of factors for risk stratification of at-risk individuals for CRC, and have implications to identify novel therapeutic targets.

**Aim 1: To establish the “field” inflammatory profile associated with alcohol and wrong-time feeding-induced carcinogenesis**

**Rationale:** We showed that circadian disruption in mice, using either genetic (*Clock*Δ19 mutant) or environmental models (light:dark shift), promotes alcohol-induced intestinal inflammation. Our data similar to prior studies, show that wrong time eating causes intestinal circadian disruption in mice [Fig 2], and can augment alcohol’s effect on colon carcinogenesis [Fig 1]. Here, we will do an in-depth analysis of mucosal and polyp immune profiles (using immuno-staining and RNA-Seq), associated with enhanced carcinogenesis to alcohol and wrong time eating. The generated library will be used in Aim 3.

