
**Anticipated results, potential pitfalls, alternative approaches, future directions:** We hypothesize that delayed eating, while keeping calorie intake, food component, sleep-wake and activity levels stable, will promote alcohol-induced disruption of the peripheral circadian rhythm, and enhance central/peripheral circadian dyssynchrony. We expect delayed eating with alcohol to exhibit a phase shift in the expression of digestive tract clock genes (buccal mucosa) in relation to the central circadian rhythm assessed by the timing of melatonin rhythms relative to sleep (dim light melatonin onset, DLMO). Given our preliminary data, we expect to see alcohol effects on peripheral and central circadian rhythms. The expected enhancement of the deleterious effects of alcohol on circadian rhythms in humans by delayed/abnormal eating will have a significant impact beyond the cancer field, given the commonality of both habits, and the broad-spectrum of alcohol-associated diseases. It is possible that diet composition may affect circadian rhythms in the intestine.

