
**Statistics and Overview of data analysis.** A sample size of 44 achieves 81% power to detect 0.1 mean changes in circadian rhythm profiles measured by melatonin and circadian gene expression and changes in immune gene expression and carcinogenesis markers (proliferation, apoptosis and DNA markers) within a subject with an estimated standard deviation of differences of 0.3 under a significance level (alpha) of 0.05 using a two-sided paired t-test. Power will be increased by using multivariable regression including other covariates that may affect the outcomes including demographics such as gender, BMI, age, race and chronotype. Repeated Measure ANOVA with two factors (alcohol, eating pattern) and their interaction (alcohol\*eating) will be used. To control various types of additional predictors other than alcohol and eating conditions, a Generalized Estimating Equation (GEE) model approach will be used.

**I. Generation of immune profiles in response to alcohol and abnormal food timing:** In Aim 1, RNA-seq, will be done to infer Treg/Th17/neutrophil profiles, associated with worsening polyposis in response to alcohol and abnormal eating patterns (or each alone). The immune signature will be used for profiling the gene expression data from mucosal biopsy tissues obtained in Aim 3a.

**II. Immune profiling from sigmoid tissue:** In Aim 3a, RNA-seq will be done on biopsies followed by immune profiling using CIBERSORT. Immune signatures determined in Aim 1a will be used as a guide to interrogate the profiles obtained from endoscopic sampling in response to alcohol or delayed food timing, or both.

**III. Microbial composition and structure:** 16S rRNA amplicons will be sequenced using an Illumina MiSeq instrument, with an anticipated output of 50,000 sequences per sample. The surveys of microbial genes generated by deep-sequencing will be used for microbial composition profiling using the Bioconductor R package metagenomicSeq and diversity analysis with the Shannon’s index using the

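### The stated 81% power does not follow from its own inputs (they give 58%), and no power is given for the alcohol-by-eating interaction that tests the cofactor hypothesis

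*Protocol*

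**What the plan says.** The only power statement is in the paragraph Statistics and Overview of data analysis, at the end of Protocol section C:

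- Power, sample size and change: "A sample size of 44 achieves 81% power to detect 0.1 mean changes in circadian rhythm profiles". The sentence extends the same figures to immune gene expression and to the proliferation, apoptosis and DNA-damage markers.
- Variability: "within a subject with an estimated standard deviation of differences of 0.3".
- Test: "under a significance level (alpha) of 0.05 using a two-sided paired t-test".

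The same paragraph then names the analysis: "Repeated Measure ANOVA with two factors (alcohol, eating pattern) and their interaction". No effect size, standard deviation or power is attached to the interaction term.

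On design, section B says "Our human study will use a crossover, 2 by 2, design to examine the same individual under 4 conditions". On the question asked, section A states the hypothesis that "a delayed eating pattern is a key cofactor that increases susceptibility to alcohol-induced colon carcinogenesis", and the anticipated results of Aim 2 say that delayed eating "will promote alcohol-induced disruption of the peripheral circadian rhythm, and enhance central/peripheral circadian dyssynchrony". Section C also says that the study will determine "the effect of the combination (as well as each separately) of alcohol consumption and delayed eating".

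**The concern.** There are two faults, and they should be kept apart.

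The first is a calculation error. The power sentence fixes every input of a paired t-test, so its result can be checked directly, and 81% is not that result.

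The second is a gap. A cofactor hypothesis says that alcohol's effect is larger under delayed eating than under right-time eating. In this four-condition crossover that is a difference between two within-subject differences, which the planned ANOVA tests as the interaction. A power figure for one paired difference, right or wrong, does not describe that test.

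What is at stake is how a null result will be read. The Human Subjects section (4.1.1a) says that if no influence of eating pattern on alcohol's effect is seen in these susceptible hosts, the hypothesis need not be tested in healthy subjects. A reader told that the study has 81% power would accept that inference more readily than the design allows.

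**Working it through.** **Inputs from the statistics paragraph.** n = 44, mean within-subject change δ = 0.1, SD of differences σ_d = 0.3, two-sided α = 0.05, paired t-test.

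**Step 1: the plan's own figure.** The noncentrality is (δ/σ_d) × √n = (0.1/0.3) × √44 = 2.211. With 43 degrees of freedom the critical value is 2.017. Power from the noncentral t distribution is **58.0%**. The normal approximation agrees: Φ(2.211 − 1.960) = 59.9%. The stated 81% is not reproduced.

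**Step 2: what the same test would need.**

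| Quantity | Result |
|---|---|
| n for 80% power (0.1, SD 0.3) | 73 |
| n for 81% power | 75 |
| Change detectable with 80% power, n = 44 | 0.432 × 0.3 = 0.130 |
| Change giving 81% at n = 44, SD 0.3 | 0.131 |
| SD of differences giving 81% at n = 44, change 0.1 | 0.228 |

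**Step 3: other readings of the sentence.**

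| Reading | Power |
|---|---|
| One-sided test, n = 44 | 70.2% |
| Two-sided α = 0.10, n = 44 | 70.2% |
| All 55 recruited, two-sided | 68.0% |
| All 55 recruited, one-sided | 78.7% |
| 0.3 as per-condition SD, correlation 0.7 | 79.7% |
| Main effect averaged over two pairs (SD 0.3/√2, zero correlation between the two differences) | 86.4% |

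None gives 81%. Each also departs from what the sentence says: two-sided, α 0.05, 44 subjects, 0.3 as the SD of differences, a simple paired test.

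**Step 4: the interaction, as an illustration.** Let D1 be the alcohol effect under delayed eating and D0 the alcohol effect under right-time eating, each with SD 0.3, and let r be the correlation between them. The interaction is D1 − D0, with

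SD = 0.3 × √(2(1 − r)).

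Equal correlation between all four conditions implies r = 0, so SD = 0.3 × √2 = 0.424. The Protocol gives neither r nor an interaction size; both are assumptions here.

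For an interaction of 0.1, the noncentrality is (0.1/0.424) × √44 = 1.563 and power is **33.3%** (34.2% with the 129 pooled error degrees of freedom of a repeated-measures ANOVA). For 80% power 144 subjects would be needed. The interaction detectable with 80% power at n = 44 is 0.432 × 0.424 = 0.183.

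Varying r, with interaction 0.1 and n = 44:

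| r | Contrast SD | Power | Detectable with 80% power (0.432 × SD) |
|---|---|---|---|
| −0.25 | 0.474 | 27.7% | 0.20 |
| 0 | 0.424 | 33.3% | 0.18 |
| 0.25 | 0.367 | 42.3% | 0.16 |
| 0.5 | 0.300 | 58.0% | 0.13 |

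Varying the interaction, with r = 0 and n = 44:

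| Interaction | Power |
|---|---|
| 0.05 | 11.9% |
| 0.10 | 33.3% |
| 0.15 | 63.0% |
| 0.20 | 86.4% |

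**Step 5: are the two faults separate?** Suppose the SD of differences were the 0.228 that makes 81% correct. With r = 0, an interaction of 0.1 would then have 51.9% power. Correcting the arithmetic alone therefore does not close the gap.

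The dropout step is sound: 44/(1 − 0.20) = 55, as the Protocol says under Aim 2.

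**The case against.** The best defence is that the interaction is not declared primary. The Protocol also targets each factor separately, and its integrated-analysis text describes the effect of eating pattern among people who drink, which is one paired difference. Under equal correlation, a main effect of 0.1 averaged over both pairs has about 86% power. That is true and limits the point: the design is not weak for every question. But the power sentence describes a simple paired test, and neither a main effect nor a paired difference shows that delayed eating modifies alcohol's effect.

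A second defence is that the Protocol expects covariate adjustment for characteristics such as gender, age and BMI to add power. This does not rescue 81%, which is attributed to the unadjusted paired t-test. Covariates that are constant within a subject also cancel from a within-subject difference, unless they explain why the difference itself varies between people.

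A third is that 0.3 may have been meant as the SD within a condition. With a correlation a little above 0.7, power would be near 81%. The text says SD of differences and gives no correlation, so this is at most a guess at how the error arose.

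Two stronger readings are tempting. A reader might infer that 81% is right for a paired difference and falls to 33% only because of the interaction. That is not so: 81 to 58 is miscalculation, and only 58 to 33 comes from the contrast. A reader might also infer that the plan's own inputs give 33%. They do not: the interaction size and r are added assumptions. At r = 0.5 the contrast is no more variable than a paired difference, and above 0.5 it is less variable.

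**Conclusion.** The concern holds in two parts of different strength.

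The first needs no added assumption: the stated inputs give 58% power, not 81%. To keep the 0.1 and 0.3, the test needs about 73 subjects for 80% power. To keep 44 subjects, the detectable change is about 0.13, or 0.43 SD of the differences.

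The second is that no power is stated for the interaction, although the cofactor hypothesis rests on it in substance. About 33% is a fair illustration for an interaction of 0.1 under equal correlation. It should always be given with its range: 28% to 58% over r from −0.25 to 0.5, and 12% to 86% over interactions from 0.05 to 0.2 at r = 0. The documents do not support saying that the interaction is the only hypothesis, or that 33% is the power of the study.

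**What to change.** Keep 44 completers and replace the power sentence with three statements:

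1. A two-sided paired t-test at 0.05 with 44 subjects has 58% power for a change of 0.1 when the SD of differences is 0.3; equivalently, it has 80% power for a change of about 0.13 (0.43 SD of the differences).
2. With 44 subjects, the alcohol-by-eating interaction detectable with 80% power is about 0.18, assuming equal correlation between conditions (contrast SD 0.424), and ranges from about 0.20 to 0.13 if the two simple differences correlate from −0.25 to 0.5.
3. A non-significant interaction will be interpreted through its confidence interval and not as absence of effect.

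If the sponsor has a source for a smaller SD of differences, about 0.228, citing it would restore 81% for the paired test; the interaction statement would still be needed and should be recomputed with that SD.

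The cost is Protocol wording only, with no change to recruitment or procedures. The downside is that the stated figure becomes less favourable.

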**Anticipated results, potential pitfalls, alternative approaches and future**

**directions:** Our prelim data support our hypothesis that abnormal eating promotes alcohol-induced carcinogenesis. Our published data support our expectation of seeing an enhanced mucosal inflammation due to alcohol and circadian dysrhythmia. In light of the key roles of Treg/Th17, and neutrophil signaling in CRC, we expect to see an imbalanced profile (e.g., a decreased Tregs, an increased Th17 response, increased neutrophils or an altered ratio) due to combined effects

Abnormal Food Timing and Circadian Dyssynchrony in Alcohol Induced Colon Carcinogenesis

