the prior three months, to exclude subjects on special diets (e.g., vegetarian, gluten-free) and recruit individuals who meet criteria for a typical American diet consisting of daily fiber  $\leq$  16 grams and daily saturated fat  $\geq$  11 grams. All subjects will be  $\geq$  21 years old [expected to be over 50 years old because of a history of polyps], and will be recruited after reviewing the endoscopy database of Rush University's Gastroenterology Division. Exclusion/inclusion criteria, definition of AUD and advanced adenoma are described in Human Subjects. Subjects are asked to avoid any alcoholic drinks for one week prior to each study. One week prior to the study, subjects complete the food/sleep questionnaire/(FSQ) (see Human Subjects) to record baseline food/sleep patterns. Sleep patterns will also be recorded by wrist actigraphy (Actiwach 2, Phillips Inc.). Each subject will undergo four conditions (each for one week in duration with a week wash-out in between [Fig 7]. The order of experiments will be randomized [concealed randomization]. A 24h food recall will be completed by participants using ASA24 at baseline and once during each intervention. This will be used to both determine that dietary intake is kept constant throughout the study, but also to verify time of eating on the FSQ in each of the treatment periods. "Right-time eating" is defined as breakfast (no later than 8am), lunch (no later than 1pm) and dinner (no later than 6pm), while "delayed eating" will be applied by delaying each meal by 3h. The choice of 3h is based on prior reports that alteration in the meal time for 3h can affect weight. Subjects will continue their regular energy and macronutrient content. All attempts will be made to keep sleep-wake periods constant between 11pm and 7am  $\pm$  2 hours. The limit of 2 hours was selected because sleep/wake periods over 2 hours would lead to disrupted circadian rhythms. Adherence to the protocol will be monitored via the FSQ. Subjects will enter the Biological Rhythms Research Lab after each week of the intervention period for 24h for assessments of central circadian rhythms (hourly salivary melatonin) and peripheral clock genes of the digestive tract from mucosal cells taken from buccal swaps once every 2h (12 time points). Extracted cells will be analyzed for expression levels of clock genes (*Per2*, *BMAL1*, *Clock*, *Cry1*, *Reverb-alpha*, *ROR-alpha*). While frequent endoscopic sampling of the intestine is not practical in humans, frequent buccal sampling is the most feasible method to assess the intestinal circadian rhythm^86. Further, using buccal sampling is an acceptable method to assess the digestive tract rhythm, as the intestinal cells have common zeitgebers (SCN, food and GI hormones). Nonetheless, we will also collect rectal swab every 12 hours (2 time points; first sample at the time of sigmoidoscopy) to validate that buccal sample represent disruption of digestive tract circadian rhythmicity by delayed eating. Our prelim data show feasibly of RNA analysis of clock genes from rectal swabs (Fig 8). The observed reciprocal RNA expression of the clock positive limb (*Bmal1* and *Clock*) vs. negative limb (*Per2* and *cry1*) members is suggestive of an expected anti-phasic pattern. Rectal swab sampling more than twice is not practical. Although the rhythm of proximal part may phase-advance the distal part of the digestive tracts, rhythm of different segments of GI tracts are still in synchrony to maintain a healthy physiologic homeostasis. Therefore buccal rhythm, though not a direct predictor of colonic rhythm, fits our purpose of assessing alteration of digestive tracts rhythm of subjects in response to our intervention (alcohol or food timing). For alcohol-related experiments, subjects will be given bottles of red wine and asked to drink wine with dinner (0.5 g/kg) for the week prior to the Lab visit. We have shown that this protocol causes disruption of circadian genes in PBMC [Fig 6] and promote systemic inflammation (unpublished data). To increase compliance, each subject is given enough bottles of wine to share with his/her partner at dinner.

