affected by bowel-cleansing products) no bowel preparation will be used prior to sigmoidoscopy. All mucosal biopsies are collected from the sigmoid area (20cm from the anal verge) to minimize inherent regional differences among markers of interest. A total of 20 mucosal biopsies are obtained (n=8 RNA-seq, n=4 IHC staining, n=8 for future/alternative approach). We have taken 20 sigmoid biopsies / person in our prior studies in over 500 subjects with no complications. IHC will be done for Ki-67(mucosal proliferation as the early step in carcinogenesis), Caspase-6 (apoptosis) and gamma-histone-2AX (DNA damage). Several crypts per slide will be screened to calculate average densities of each marker to compare between pre and post-interventions in each subject. For IHC, sections of 50 microns will be cut and deparaffinized as we did previously. RNA-seq samples taken from each patient will be interrogated in several ways. First, we will use CIBERSORT to infer the Th17/Treg/Neutrophils profiles in response to delayed eating, or alcohol, or both. We will use a gene coexpression approach applied to the RNAseq data to robustly define molecular systems whose activity is affected by alcohol and circadian interventions. Gene coexpression is based on synchronized gene expression across multiple samples; it represents the activity of many regulatory mechanisms, shows tissue-specific results and has the robustness of pathway-level results. It is particularly appropriate for the emphasis on this project on synchronization, because gene coexpression is based on synchronized expression and represents biological processes across time and tissue location in an organism^106. This approach allows us to focus on robust biological processes active in the tissue, through “coexpression modules” which are groups of transcripts to see how these are related to alcohol and circadian rhythm.

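### One alpha of 0.05 and one power figure serve all circadian, immune and carcinogenesis outcomes, and the protocol names no outcome or contrast as primary

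*Protocol*

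**What the plan says.** All statements are in the protocol.

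- **Sizing** (section C, Statistics and Overview of data analysis): "A sample size of 44 achieves 81% power to detect 0.1 mean changes", "within a subject with an estimated standard deviation of differences of 0.3", "under a significance level (alpha) of 0.05 using a two-sided paired t-test". One sentence applies these inputs to "changes in circadian rhythm profiles measured by melatonin and circadian gene expression and changes in immune gene expression and carcinogenesis markers", and it lists the carcinogenesis markers as proliferation, apoptosis and DNA markers.
- **Analysis model** (same paragraph): a repeated-measures ANOVA with alcohol, eating pattern and their interaction, and a GEE model for further predictors. No alpha is stated for these models.
- **Aim 2 outcomes** (Aim 2, Methods): hourly salivary melatonin, and buccal swabs of which the protocol says "Extracted cells will be analyzed for expression levels of clock genes". Six genes are named.
- **Aim 3 outcomes** (Aim 3, Methods): Th17, Treg and neutrophil profiles inferred from RNA-seq, and tissue staining: "IHC will be done for Ki-67(mucosal proliferation as the early step in carcinogenesis), Caspase-6 (apoptosis) and gamma-histone-2AX (DNA damage").
- **Follow-on decision** (section 4.1.1a): if the study shows no effect of eating pattern on what alcohol does to colon carcinogenesis, healthy subjects need not be studied.
- **Circadian visit**: the Aim 2 Methods describe the 24-hour laboratory stay as part of the study. Section 4.1.1a and the Subject data section make it optional.

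None of these places ranks the outcomes.

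**The concern.** An alpha of 0.05 limits the error of one test, and a power figure belongs to one outcome, one contrast and one standard deviation. Here both are attached to a list of biologically different measures, as if a change of 0.1 with a standard deviation of 0.3 meant the same for melatonin, a clock gene and Ki-67. Nothing says which of them answers the question of each aim.

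Two things are at stake. First, with several outcomes and no ranking, the chance that some outcome shows a false effect exceeds 5%, and the protocol gives the reader no basis for discounting it. Second, the decision on studying healthy subjects depends on whether an effect on carcinogenesis is shown, but the deciding marker is not stated. The choice could be made after the results are seen.

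This is a protocol matter. The sample size is fixed here, so the test it is meant to serve should be fixed here too.

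**Working it through.** **1. The plan's own power figure.** Inputs from the statistics paragraph: n = 44, mean change 0.1, SD of differences 0.3, two-sided alpha 0.05, paired t-test.

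- Noncentrality = (0.1 / 0.3) × √44 = 2.211; critical t on 43 df = 2.017.
- Power = 58.0% (exact noncentral t) or 59.9% (normal approximation), not 81%.
- For 81%, one would need 75 subjects, or an SD of differences near 0.228, or a change near 0.131.

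**2. Count of outcomes.**

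- In the power sentence: melatonin, circadian gene expression, immune gene expression, proliferation, apoptosis and DNA damage, so 6.
- Spelled out from the Aim 2 and Aim 3 Methods: melatonin (1), clock genes (6), Th17, Treg and neutrophils (3), Ki-67, Caspase-6 and gamma-H2AX (3), so 1 + 6 + 3 + 3 = 13.

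**3. Chance of at least one false positive.** Assumptions: one interaction test per outcome, each at two-sided 0.05, and no true effect on any outcome. The 0.05 is carried over from the paired t-test, because it is the only level the protocol states.

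- Independent outcomes: 1 − 0.95^k. For k = 6, 1 − 0.95^6 = 26.5%. For k = 13, 1 − 0.95^13 = 48.7%.
- Equally correlated outcomes (normal test statistics, cut-off 1.96). The correlation is an assumption, so a range is shown:

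| Pairwise correlation | 13 outcomes |
|---|---|
| 0 | 49% |
| 0.3 | 42% |
| 0.5 | 33% |
| 0.7 | 24% |
| 0.9 | 14% |

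Simulated t-tests with n = 44 agree to within about one percentage point (for example 34% at 0.5 and 25% at 0.7).

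**4. Power for the contrast that carries the hypothesis.** The interaction is a difference of two differences: the alcohol effect under delayed eating minus the alcohol effect under right-time eating. If each difference has SD 0.3 and their correlation is r, the contrast SD is 0.3 × √(2(1 − r)). The protocol gives no r.

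- r = 0 (assumption): SD = 0.3 × √2 = 0.424; noncentrality = (0.1 / 0.424) × √44 = 1.56. Power is 33% at alpha 0.05 and 23% at 0.025.
- r = 0.5: SD = 0.3, so power is the same as for the simple contrast, 58% at 0.05 and 46% at 0.025.

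All of these use n = 44. For outcomes from the optional 24-hour assessment the number may be smaller.

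**The case against.** **A reader might infer that any single outcome crossing 0.05 would count as success.** The protocol states no such rule. The wording that seems to say so, "a decreased Tregs, an increased Th17 response, increased neutrophils or an altered ratio", is in the anticipated results of Aim 1, which uses stored mouse tissue. For the human study, the anticipated results of Aim 3 describe several changes together: immune imbalance, hyperproliferation and reduced apoptosis. The error rate for at least one outcome would be the wrong measure if all were required. This part of the objection stands. However, the protocol does not say that all must occur, and it leaves the immune imbalance undefined.

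**A reader might quote 33% to 49% as the range.** That holds only for 13 tests with correlation between 0 and 0.5; 33% is not a floor. The protocol expects immune, proliferative, microbial and circadian changes to correlate, and it reports reciprocal expression among clock genes. The count of 13 also treats six genes as six endpoints, whereas the Aim 2 expectation is closer to one construct, clock-gene phase relative to melatonin onset. Likewise 1 − 0.95^39 = 86%, for three effects on 13 outcomes, assumes that all 39 tests are independent and that each can decide.

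**Multiplicity methods belong in the SAP.** Agreed; their absence here is no finding. The missing primary outcome, and a sample size that claims to serve every outcome, remain.

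**The project is mechanistic and early-stage.** This lowers the severity. It does not make one alpha and one power figure valid for an unranked list.

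**Conclusion.** The point holds as a should-fix. The protocol sizes the study once for all human outcomes and designates none as primary, so the stated alpha and power describe one pre-chosen test and not the trial's overall claim. The false-positive chance over the 13 named interactions is up to about 49%, and still about 14% at correlation 0.9, nearly three times the nominal 5%. These figures rest on no true effect on any outcome, one interaction test per outcome, and the use of 0.05 for the interaction, which is inferred. The documents do not support a stronger statement that the protocol adopts an any-outcome rule.

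The shared power figure is also wrong on its own inputs: 58% against the stated 81%. For an interaction with uncorrelated component differences it is about 33%. That last figure depends on the assumed correlation between the differences.

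**What to change.** In the statistics paragraph:

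1. Name one primary test for each human aim before data are seen. Candidates already in the protocol are the alcohol by eating interaction on Ki-67 for Aim 3, and the same interaction on buccal clock-gene phase relative to dim light melatonin onset for Aim 2. The sponsor may choose others.
2. Label all other outcomes secondary or exploratory. The multiplicity method for them may be left to the SAP.
3. Tie the statement that the hypothesis is supported, and the decision about healthy subjects in section 4.1.1a, to the primary tests.
4. Replace the single power sentence with power for each primary test as an interaction contrast. Give an SD specific to that outcome, the assumed correlation between the two differences, and the alpha used (0.05 for each aim, or 0.025 if the two tests share it).
5. For the Aim 2 test, base power on the number expected to complete the 24-hour assessment, and reconcile the sections that differ on whether that assessment is optional.

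The change is to wording only and adds no visit or sample. The cost is a less favourable stated power. On the printed inputs it is 58% for a simple paired contrast at 0.05, and 33% (at 0.05) or 23% (at 0.025) for an interaction with uncorrelated differences. The sponsor would then have to justify the sample size again or present the study as exploratory.
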